4.0 Abstract

Title: Real-World Outcome of Adalimumab on Rheumatoid Arthritis Patients in China

Rationale and Background: Given the requirement to keep a balance between effectiveness and cost containment to ensure that the available health resources are used in a cost-effective manner, there is an increasing demand for real-world evidence (RWE) from policy makers, regulators, providers and payers in the region to optimize spending and patient outcomes.

So far, there are no data available regarding adalimumab's impact on patients' quality of life (QoL) and healthcare resource utilization (HCRU) in a realistic study design, which provides greater generalization in China.

The goal of this study is to determine the QoL, HCRU and costs of the patients care in subjects with RA who are treated with adalimumab in China.

Results from study on the effect of adalimumab on Work Productivity and Activity Impairment (WPAI) scores and other Patient-Reported Outcomes (PROs) will be of interest to a variety of stakeholders in the healthcare system including patients, healthcare practitioners and payers in China.

Research Question and Objectives: The objective of this non-interventional, observational study is to assess the effect of adalimumab on health-related QoL and work productivity in patients with Rheumatoid Arthritis (RA) in China. Specifically, to achieve the above objective the following concrete steps will be taken:

1. Recruit investigators who are willing and able to recruit and follow new adalimumab users for 6 months follow-up
2. Collect the patients' clinical profile, patient-reported QoL, functioning, work productivity, treatment satisfaction and HCRU of RA patients at adalimumab initiation
3. Follow the patients initiating adalimumab for 24 weeks and identify the changes in clinical, economic, and PROs associated with adalimumab

Study Design: The study is designed as a prospective, observational study to assess the effect of adalimumab on health-related QoL and work productivity in patients with RA in China.

RA patients, for whom adalimumab treatment has already been decided as per local label, will be recruited from within the clinical settings of each rheumatologist participating in the study. Approximately 52 patients diagnosed with RA that meet the inclusion and exclusion criteria will be enrolled at approximately 16 sites.

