The Health Assessment Questionnaire Disability Index (HAQ DI) data will be collected at baseline, Week 12 and Week 24 after treatment initiation with adalimumab, as per standard daily clinical practice. In addition, when available, other PROs of work activity and well-being, including the WPAI, EuroQol 5 dimension (EQ-5D), and Short Form 36-Item Health Survey (SF-36), will also be collected.

In addition, when available, the health care resource utilization will be collected. This includes surgical procedures, hospitalizations, bed days in hospital, physician consultations etc. Costs will be assigned based on the health care resource utilization using standardized costs for China.

Note: This study is non-interventional and the subjects/investigators will follow the current clinical practice in each site and also the routine clinical follow up as determine by the treating physician.

Population: Subjects will be males and/or females who are attending a routine clinical visit and meet all of the inclusion criteria and none of the exclusion criteria. Approximately 52 patients diagnosed with RA will be recruited.

Main Inclusion Criteria:

Patients meeting all of the following inclusion criteria at baseline will be included:

1. Subject has a diagnosis of RA as defined by the 1987 revised American College of Rheumatology (ACR) classification criteria and/or the ACR/the European League against Rheumatism (EULAR) 2010 classification criteria (any duration since diagnosis).
2. Male or female subjects ≥ 18 years of age who is in compliance with eligibility for adalimumab based on the local label.
3. Patients with moderate to severe RA defined as Disease Activity Score in 28 Joints (DAS28) (ESR) or DAS28 (CRP) > 3.2
4. Biologically treatment naïve and initiated adalimumab at baseline visit, as per standard daily clinical practice.
5. Availability of clinical data of the previous 12 weeks prior to baseline
6. Ability to self-complete patient questionnaires
7. Patients have signed the authorization (or informed consent where applicable) to disclose and use personal health information after been prescribed with adalimumab.

Main Exclusion Criteria:

Patients meeting any of the following exclusion criteria at baseline will be excluded:

1. Patients who are pregnant or breast feeding at enrolment or wish to become pregnant in the next 24 weeks.

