9.0 Research Methods

9.1 Study Design

This study is designed as a prospective, observational study to assess the effect of adalimumab on health-related QoL and work productivity in patients with RA in China in clinical practice.

The study population will include Chinese adult patients with a diagnosis of RA who meet the requirements per the local label for treatment with adalimumab at the baseline visit. The decision to prescribe adalimumab for RA should be based on clinical practice criteria without taking participation in this study into account. Patients will be included in the study after a physician's decision of initiating Humira.

Approximately 52 patients diagnosed with RA that meet the inclusion and exclusion criteria will be enrolled at approximately 16 sites.

This study is non-interventional and the subjects/investigator will follow the current clinical practice in each site. Not additional task will be required other than current practice to keep the data as "real world data collect".

The observation period for each patient is 24 weeks. All visits are to be scheduled as per routine clinical practice, regardless of study participation. Patients may discontinue adalimumab treatment or the study at any time without prejudice.

The physician will follow the patient during regular clinic visits at intervals as determined by routine clinical practice. Data at the clinic visits within ± 7 days of the study-defined time points will be collected and data at the clinic visits closest to the study-defined time points will be used for statistical analysis (If there are 2 clinic visits equidistant from a study-defined time point which do not correspond to any other visit, data from the EARLIER clinic visit shall be used for the study-defined time point).

The HAQ DI data will be collected at baseline, Week 12 and Week 24 after treatment initiation with adalimumab, as per standard daily clinical practice. In addition, when available, other PROs of work activity and well-being, including the WPAI, EQ-5D, and SF-36, will also be collected.

The HCRU will also be collected, when available. This includes surgical procedures, hospitalizations, bed days in hospital, physician consultations etc. Costs will be assigned based on the HCRU using standardized costs for each participating countries.

Primary Endpoint

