8. If female subject, is either not of childbearing potential, defined as postmenopausal for at least 1 year or surgically sterile (bilateral tubal ligation, bilateral oophorectomy and/or hysterectomy) or is of childbearing potential and is practicing an approved method of birth control throughout the study and for 150 days after last dose of study drug.
9. Subject is judged to be in good health as determined by the Principal Investigator based upon the results of medical history, laboratory profile, physical examination, chest x-ray (CXR), and a 12-lead electrocardiogram (ECG) performed during Screening;
10. Subject has a negative TB Screening Assessment. If the subject has evidence of a latent TB infection; the subject must initiate and complete a minimum of 4 weeks of an ongoing TB prophylaxis or have documented completion of a full course of TB prophylaxis, prior to Baseline

9.2.2 Exclusion Criteria:

Patients meeting any of the following exclusion criteria at baseline will be excluded:

1. Patients who are pregnant or breast feeding at enrolment or wish to become pregnant in the next 24 weeks
2. Participation in any RA-related clinical trial at the time of enrolment, at baseline or at any point during the past 24 weeks prior to baseline
3. Patients, who in the clinician's view, may not be able to accurately report their QoL or prior resource utilization
4. Patients, who in the clinician's view, may not be able to adhere to adalimumab therapy over 24 weeks

Additional Exclusion Criteria

5. Subject has been treated with any investigational drug of chemical or biologic nature within a minimum of 30 days or five half-lives (whichever is longer) of the drug prior to the Baseline Visit
6. Prior exposure to biologics that have a potential or known association with PML (i.e., natalizumab (Tysabri®), or rituximab (Rituxan)
7. Positive pregnancy test at Baseline
8. Patients with contraindication or are not appropriate to use adalimumab according to local label or investigators' judgment

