The WPAI is a patient-reported questionnaire to measure work and activity impairment during the past seven days. It determines employment status, hours missed from work due to the disease (i.e. RA), hours missed from work for other reasons, hours actually worked, the degree to which the disease affected work productivity while at work and the degree to which the disease affected activities outside of work. Additional questions around employment status will be incorporated into the survey. The completion time for the WPAI is approximately 2-5 minutes. The full version of WPAI is presented in **Error! Reference source not found.**

All of the above questionnaires will be used with the validated Chinese version.

Patient Global Impression of Change (PGIC)

The PGIC measures the patient's perceptions of changes in their disease. It consists of one question asking about the change in their condition; for this study, the base will be "since you initiated your adalimumab treatment". The completion time for the PGIC is less than 1 minute. The full version of PGIC is presented in **Error! Reference source not found.**

Patient Treatment Satisfaction Questions

The patient treatment satisfaction questions were developed de novo for this study and are not considered "validated" questions. Self-administered by the patient, the completion time for the patient treatment satisfaction questions is approximately 1-2 minutes. The full version of patient treatment satisfaction questions are presented in **Error! Reference source not found.**

Healthcare Resource Utilization (HCRU) Questionnaire

The HCRU questionnaire will collect data on the healthcare resources consumed in the prior 3 months, as recall beyond 3 months may be problematic in an older population (16). HCRU collection will include data such as the number of physician visits and to which physician (GP, specialist), Emergency Department visits, hospitalizations, and other drugs as well as devices and aids purchased to assist in their mobility due to RA. The HCRU questionnaire will be part of the patient questionnaire and will be distributed to patients together with the PRO questionnaires (Appendix D to Appendix I). The full HCRU questionnaire is presented in **Error! Reference source not found.J** and will be used with the validated Chinese version.

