### **3. STUDY DESIGN**

#### **3.1 Overview of Study Design**

This study is designed as a prospective, observational study to assess the effect of adalimumab on health-related QoL and work productivity in patients with RA in China in clinical practice.

This study is non-interventional. Patient therapy is not decided by the study protocol but falls within current medical practice, and the prescription of adalimumab is clearly separated from the decision to include the patient in this study. The subjects/investigator will follow the current clinical practice in each site and also the routine clinical follow up as determined by the treating physician.

RA patients will be recruited from within the clinical settings of each rheumatologist participating in the study. Approximately 55 patients diagnosed with RA that meet the inclusion and exclusion criteria will be enrolled at up to 8 sites in China.

To assess health and disability outcomes, the HAQ DI will be assessed at baseline, Week 12 and Week 24 after treatment initiation with adalimumab. In addition, other PROs of work activity and well-being, including the WPAI, EQ-5D-3L, and SF-36,

will also be collected. All above instruments have been validated for the Chinese version.

The patients identified by the recruiting investigators based on the study selection criteria will complete a set of patient questionnaires on QoL, functioning, work productivity, treatment satisfaction, impression of change and HCRU. Data will be captured at baseline (D0), Week 12 and Week 24.

The HCRU will also be collected. This includes surgical procedures, hospitalizations, bed days in hospital, physician consultations etc. Costs will be assigned based on the HCRU using standardized costs for each participating centers.

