### **3.5 Definitions of Study Variables**

The key variables of interest in this study are demographic and clinical characteristics, patient-reported health and disability outcomes, and healthcare resource utilizations. Most variables will be measured at baseline (i.e. index), and at weeks 12 and 24 after

the initiation of Adalimumab; healthcare resource utilization will be summarized over the 6 month post-index period.

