## 5.5 Analysis Plan for Exploratory Objectives

- Excel Table 7 describes the change in 4 patient satisfaction questions at weeks 12 and 24 after the initiation of adalimumab, in those patients continuing on adalimumab (observed population). These changes will be summarized as number and percentage of each response and compared with Wilcoxon signed rank test. Satisfaction will also be dichotomized and analyzed over time with Cochran-Armitage test for trends.
- Excel Table 8 summarizes the patients' global impression of change in RA at weeks 12 and 24 after the initiation of adalimumab, in those patients continuing on adalimumab (as observed population). Each response (very much better, much better, a little better, no change, a little worse, much worse, and very much worse) will be summarized as number and percentage.
- Descriptive statistics will be presented for post-index overall RA related direct healthcare resource utilization (Excel Table 9)
  - Consultations/visits to healthcare professionals for treatment of RA (number of patients with  $\geq 1$  visit; categorized by the treatment department listed in 3.5.4)
  - Procedures received when visiting the healthcare professional(s) for treatment of RA (number of patients with  $\geq 1$  procedure; categories listed in 3.5.4)
  - surgeries received when visiting the healthcare professional(s) for treatment of RA (number of patients with  $\geq 1$  surgery; categories listed in 3.5.4)
  - Hospitalizations in relation to RA (number of patients with  $\geq 1$  admission)
  - Length of stay in days (mean, SD, median)
  - Concomitant medications taken for RA (number of patients with  $\geq 1$  medication; categories listed in 3.5.4))

- Associations between disease severity (measured by DAS28) and PROs (HAQ DI score, SF-36 domain scales, EQ-5D-3L index, WPAI outcomes) will be analyzed using the bivariate linear regression model (Excel Table 10.1). Separate models will be estimated to identify the association between DAS28 and each of the PROs. If normality assumption for the residual of regression is violated, Spearman correlation coefficients and p-values will be estimated instead.

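### Costs are a stated goal but no cost analysis is specified, and SAP 5.5 replaces the resource counts that costing needs with the number of patients having at least one event

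*SAP*

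**What the plan says.** The protocol Abstract (4.0) sets the aim: "The goal of this study is to determine the QoL, HCRU and costs of the patients care in subjects with RA". Costing is then announced three times:

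- Protocol Abstract: "Costs will be assigned based on the health care resource utilization using standardized costs for China".
- Protocol 9.1: "Costs will be assigned based on the HCRU using standardized costs for each participating countries".
- SAP 3.1: "Costs will be assigned based on the HCRU using standardized costs for each participating centers".

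On resource use, protocol 9.2.4.7 states that "The HCRU questionnaire will collect data on the healthcare resources consumed in the prior 3 months", including how many physician visits were made and to which kind of physician. Protocol 9.7.6 and SAP 2.3 plan a number and percentage within categories that are themselves counts (consultations, procedures, surgeries, hospitalisations, concomitant medications), together with length of stay. SAP 3.5.4 defines the derived variables as numbers of each.

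SAP 3.5 adds that "healthcare resource utilization will be summarized over the 6 month post-index period". SAP 5.5, which specifies Table 9, turns the first item into "Consultations/visits to healthcare professionals for treatment of RA (number of patients with" at least one visit. It uses the same at-least-one form for procedures, surgeries, admissions and medications. Length of stay is the exception, with mean, SD and median.

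**The concern.** The rationale in protocol 7.0 and SAP 1.1 is evidence for payers and for critical disease insurance decisions. An economic aim stated in that setting should lead to an economic estimate, and as the plan is written none will be produced.

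The form of Table 9 makes this harder to repair at the reporting stage. Counts are collected and derived, but the one HCRU table in the SAP discards them for everything except length of stay. A reader of that table could not apply unit costs to it, and could not tell a patient with one consultation from a patient with ten.

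**Working it through.** The documents give no cost or HCRU figure to reproduce, so the check is a trace through the text followed by short arithmetic.

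**1. Costs from goal to output**

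| Step | Where it should appear | What is there |
|---|---|---|
| Goal | Protocol 4.0 | Costs named |
| Unit-cost basis | Protocol 4.0, 9.1; SAP 3.1 | China; participating countries; participating centres |
| Unit-cost source, price year | Either document | None |
| Cost variable | Protocol 9.3; SAP 3.5 | None |
| Cost analysis | Protocol 9.7; SAP 5 | None |
| Cost table | SAP 6, Tables 1 to 11 | None |

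In a study run only in China the first two bases come to the same thing. The conflict of substance is national against centre-level prices. With centre-level prices, cost differences between patients mix price with use; with a national tariff they reflect use alone.

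**2. Whether the Table 9 measure can be costed**

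Cost for patient i = sum over categories k of (count n_ik × unit cost c_k). Table 9 supplies only the number of patients with n_ik ≥ 1. Multiplying that by c_k gives a floor and not an estimate, because every patient with use is charged for a single event.

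**3. How much information the indicator loses**

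Assume, for illustration, a Poisson count with mean m, so that P(at least one) = 1 − exp(−m).

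| Mean events per patient | P(at least one) |
|---|---|
| 6 | 99.8% |
| 3 | 95.0% |
| 1 | 63.2% |
| 0.1 | 9.5% |
| 0.05 | 4.9% |

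Halving a frequent item from 6 to 3 moves the indicator by 99.8 − 95.0 = 4.8 percentage points. For rare items the indicator nearly equals the mean (9.5% against 0.1), so little is lost.

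**4. The rheumatologist row**

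Patients are recruited and followed in rheumatologists' clinics, so anyone giving Week 12 or Week 24 data has attended one. Take 3 months as 91 days. The nominal Week 12 recall starts at day 84 − 91 = −7 and so contains the baseline visit. The nominal Week 24 recall starts at 168 − 91 = 77 and contains the Week 12 visit. With the ±7-day windows and a 90- to 92-day recall, it still contains that visit in 84% to 91% of equally weighted day pairs. With about 47 completers (52 × 0.9 = 46.8), a result of 47/47 would have an exact 95% lower limit of 0.025^(1/47) = 92.5%.

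**5. Recall periods, which matter once counts are reported**

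- Two recalls: 2 × 91 = 182 days, against 168 days of follow-up.
- Time before baseline in the Week 12 recall: 7 days nominally, 0 to 14 across the visit window (day 77 to 91).
- Overlap of the two recalls: 91 − 84 = 7 days nominally. The interval between visits can be 70 to 98 days, which gives 0 to 21.
- Check: 182 − 168 = 14 = 7 + 7.

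**The case against.** The best defence is that nothing is lost in the data. The questionnaire asks for numbers of visits, SAP 3.5.4 derives counts and length of stay is summarised as a continuous variable, so costs could be calculated later. The number-and-percentage wording in protocol 9.7.6 also leaves some room for a proportion of patients. The table-shell workbook is not among the documents and might hold more detail. The first part stands: a reader might infer that the cost goal cannot be met, but the documents show only that its analysis is unspecified. The rest does not remove the point. Protocol 9.7.6 and SAP 2.3 name counts as the categories, SAP 5.5 drops them, and SAP 6 lists the tables with none for costs.

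Four stronger readings are tempting, and the documents do not support them.

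- **The whole table is driven to 100%.** SAP 3.5.4 splits use into many departments, procedures and surgery types. Saturation is credible for rheumatologist visits and perhaps blood samples, but not for surgeries, admissions or most other rows. Protocol 9.1 also says that visits follow routine practice, so they are real care and not only an artefact of the study.
- **Entry tests inflate the table.** The protocol requires "laboratory profile, physical examination, chest x-ray (CXR), and a 12-lead electrocardiogram (ECG) performed during Screening", which is before baseline, while Table 9 covers the time after it. SAP 3.2.1 accepts tests up to 90 days old. If test dates are assumed uniform over those 90 days, only 7% to 9% fall inside a Week 12 recall taken at day 84 (0% to 17% across the visit window). Tests done close to baseline would raise this.
- **Overlapping recall distorts the reported measure.** An at-least-one indicator over six months does not change when the same event is reported twice. The overlap matters only for summed counts.
- **The questionnaire should be re-anchored to study visits.** Planned data collection ended on 30 June 2018 (protocol 6.0), before the current SAP of 30 May 2019, so on those dates the form can no longer change.

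**Conclusion.** The point holds in two parts. First, costs are in the stated goal and are announced on three bases that do not agree, but no cost variable, source, analysis or table is specified. Second, SAP 5.5 reduces five types of resource use to at-least-one indicators although protocol 9.7.6, SAP 2.3 and SAP 3.5.4 name counts. An indicator cannot be costed, and for rheumatologist visits it says almost nothing.

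The first part and the mismatch over counts rest on the text alone. The size of the information loss rests on an assumed Poisson count with illustrative means. The recall arithmetic rests on 3 months being about 91 days and on the questionnaire following the protocol's description, since the form itself is not in the documents. The primary HAQ DI analysis is not affected. What is at stake is a stated secondary aim that would otherwise have no estimate.

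**What to change.** 1. In SAP 5.5 and Table 9, report per-patient counts (mean, SD, median) beside the number and percentage with at least one event, for each SAP 3.5.4 category, separately for the Week 12 and Week 24 recall periods. Give the number of patients contributing to each period.
2. Add a cost-per-patient table (counts × unit costs, with a 95% confidence interval). Name one unit-cost source and price year, list the components included, and reconcile protocol 4.0, protocol 9.1 and SAP 3.1 on the basis. If no such analysis is intended, remove costs from the stated goal and delete the three costing statements.
3. Do not add the two recall periods together without noting the nominal 7-day overlap and the possible capture of the baseline visit in the Week 12 recall.
4. Footnote the rheumatologist row to say that attendance is close to guaranteed for anyone giving follow-up data.

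The cost is SAP and table-shell wording, a derived cost variable and some extra programming. No new data collection is needed for the counts. The downside is that counts and costs rest on patient recall, which the report should say.

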9.5 Study Size

Approximately 52 patients diagnosed with RA will be recruited. The planned sample size provides 80% power for detecting a statistically significant improvement in HAQ-DI (Δ HAQ-DI < 0) assuming a mean Δ HAQ-DI of -0.21 and a standard deviation of 0.5 (reference 11), at two-sided significance level of 0.05 and accounting for a 10% dropout rate. The sample size also provides 99% power for detecting a statistically significant clinically meaningful improvement in HAQ-DI (Δ HAQ-DI < -0.22) assuming a mean Δ HAQ-DI of -0.5 and a standard deviation of 0.7, at two-sided significance level of 0.05 and accounting for a 10% dropout rate.

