9.7.3 Planned Methods of Statistical Analysis

All statistical tests will be two-tailed with a significance level of 0.05. Descriptive statistics will be provided. Descriptive analysis will be conducted on all key parameters and presented as mean, standard deviation, minimum, maximum, and median when continuous and as "n" and percent when categorical. Change from adalimumab initiation to 24 weeks will be calculated and evaluated for significant improvements using paired t-tests / ANOVA for parametric and Wilcoxon signed-rank for non-parametric data. Analysis will be also be conducted by severity level (moderate vs severe), disease duration quartile (to compare to prior work) and up to two (2) other subgroups. Cochran-Armitage test of trends or other similar methods may be used to compare categories of subjects.

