9.7.9 Additional Analysis

Additional analysis will explore the potential modifying effects of baseline measures on the changes in primary and secondary efficacy outcomes. These measures will include age, gender, baseline severity, and other diagnoses/co-morbidities. The analysis will specifically test for differential changes across the subgroups defined by the potential modifiers using general linear models.

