**DOCUMENT HISTORY**

| Version # | Issue Date | Author/Editor | Sections Changed | Change Summary   |
|------------------|-------------------|----------------------|-------------------------|---|
| V0.4             | 30 May, 2019      | [REDACTED]           | Section 2, 5            | 
 
1. Add median (Q1, Q3) for describing continuous variables when normality is violated.
 
2. Use Q1, Q3 to replace 95% Confidence interval of mean, due to the violation of normality.
 
3. Added paired Wilcoxon signed-rank test as an alternative test for paired t-test when normality is violated.
 
  |
| V0.3             | 24 Dec, 2018      | [REDACTED]           | Section 2, 5            | 
 
1. Added paired Wilcoxon signed-rank test as an alternative test for HAQ DI and WPAI analyses, due to the violation of normality.
 
2. Changed ANOVA to ANCOVA for sensitivity analysis of HAQ DI change, because we used continuous DAS28.
 
3. Added Spearman correlation as an alternative method for association analyses, due to the violation of normality.
 
   |
| V0.2             | 2 Jan, 2018       | [REDACTED]           | Section 2, 5            | 
 
1. Patient's impression of change in RA at weeks 12 and 24 after the initiation of adalimumab has been added in the Study Objectives and Statistical Analysis Section according to protocol.
 
2. Disease status of RA (moderate, severe, missing) has been deleted in Table 2, since it's duplicated with DAS28 categorization.
 
3. Dosage of first adalimumab injection has been deleted in Table 2, since the DOSE should be 40MG for all adults.
 
 |
| V0.1             | 8 Aug, 2017       | [REDACTED]           | All                     | Initial Version   |

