## 5.2 Analysis Plan for Demographic and Clinical Characteristics

- Descriptive statistics will be presented for patient demographics (Excel Table 1), and clinical characteristics (Excel Table 2) for all patients. The following measures will be assessed as of the patient’s baseline:
  - Patient age (mean, SD, minimum, maximum, median; categories: 18-34, 35-44, 45-54, 55-64, 65-74, 75+, missing)
  - Gender (male, female, missing)
  - Marital status (married, unmarried, missing)
  - Medical insurance type (National/Public insurance, Private insurance, Employer benefits, other, no insurance, missing)
  - Disease Activity Score in 28 joints - DAS28 (mean, SD, minimum, maximum, median; categories: Remission, Low Disease Activity, Moderate Disease Activity, High Disease Activity, Missing)
  - Number of patients with each of the comorbidities at baseline visit (See 3.5.2), and number of patients with any of these comorbidities

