- Additionally, in Excel Table 10.2, separate bivariate linear regression models will be estimated to identify the association between change in DAS28 and change in each of the PROs at 12 and 24 weeks after baseline respectively. If normality assumption for the residual of regression is violated, Spearman correlation coefficients and p-values will be estimated instead.
- In Excel Table 11, separate multivariate generalized linear models (GLM) will be estimated to test for the differential changes in primary and secondary efficacy outcomes after baseline, across the subgroups defined by the potential modifiers, including age, gender, baseline severity, and other diagnoses/comorbidities.

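### The exploratory effect-modifier models (Excel Table 11) are worded as subgroup tests for age and baseline severity with no coding given; continuous terms would match the SAP's own ANCOVA and avoid a possible loss of power

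*SAP*

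**What the plan says.** SAP 5.5 describes separate multivariable models, reported in Excel Table 11, that test for differential change in the primary and secondary outcomes "across the subgroups defined by the potential modifiers, including age, gender, baseline severity, and other diagnoses/comorbidities". Protocol 9.7.9 has the same plan: "The analysis will specifically test for differential changes across the subgroups defined by the potential modifiers using general linear models".

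Neither section gives a cut-point or a coding for age or severity. The groupings that the documents do contain are elsewhere:

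- **Severity.** Protocol 9.7.3: "Analysis will be also be conducted by severity level (moderate vs severe" and by disease-duration quartile. SAP 3.5.2 puts the boundary between moderate and severe at DAS28 5.1. Protocol 9.2.4.7 says that the recorded disease status, DAS28 and demographic data will serve to segment the population in the analysis.
- **Age.** SAP 3.5.2 lists both age at baseline and age groups, without bands. The only bands are in SAP 5.2, for the baseline demographics table: "categories: 18-34, 35-44, 45-54, 55-64, 65-74, 75+, missing".

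Elsewhere the SAP keeps severity on its full scale. The version 0.3 entry in its document history reads "Changed ANOVA to ANCOVA for sensitivity analysis of HAQ DI change, because we used continuous DAS28", and SAP 5.5 also regresses the patient-reported outcomes on DAS28 (Tables 10.1 and 10.2).

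**The concern.** Age in years and DAS28 are continuous and already collected. A cut at 5.1 treats DAS28 values of 3.3 and 5.0 as the same and 5.0 and 5.2 as different. If change follows a gradient, the cut discards information in a study with few patients to spare. The documents give no reason for categories in this model.

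There is also an inconsistency. This is a single-arm study, so the coefficient of baseline DAS28 in a model of HAQ DI change is itself the modifying effect of severity. The ANCOVA in SAP 5.3 estimates it on the continuous scale. If Table 11 then asks the same question of the same outcome with moderate versus severe, the report could carry two different answers, with no rule for which one stands.

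At stake is an exploratory statement about which patients improve more. A real gradient would more often be reported as no modifying effect.

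**Working it through.** **Inputs from the documents.** Protocol 9.5: "Approximately 52 patients diagnosed with RA will be recruited", "assuming a mean Δ HAQ-DI of -0.21 and a standard deviation of 0.5", "at two-sided significance level of 0.05 and accounting for a 10% dropout rate". Evaluable patients: 52 × 0.9 = 46.8, about 47. Protocol 9.7.3 applies a two-sided 0.05 level to all tests.

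**The plan's own figure.** Paired t-test, standardised effect 0.21/0.5 = 0.42, noncentrality 0.42 × √47 = 2.88. Power is 80.5% at 47 patients and 79.6% at 46, so the stated 80% is reproduced. The documents state no power for Table 11.

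**Assumptions.** The documents give no size for any modifying effect and no expected severity split. I assume a normally distributed modifier, a linear gradient with correlation r between modifier and change, and one modifier tested at a time.

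**Severity cut in two.** Power of the 1-df test comes from the noncentral F distribution with 1 and 45 df and λ = n·r²/(1 − r²). A cut that puts a share p of patients on one side multiplies r by φ(z_p)/√(p(1 − p)):

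- 50/50: 0.3989/0.5 = 0.798, keeping 64% of the explained variance
- 20/80: 0.2800/0.4 = 0.700, keeping 49%

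Example at r = 0.3:

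- Continuous: λ = 47 × 0.09/0.91 = 4.65, power 56.0%.
- 50/50: r falls to 0.239, λ = 2.86, power 38.0%.
- 20/80: r falls to 0.210, λ = 2.17, power 30.2%.

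| Assumed r | Continuous | Cut 50/50 | Cut 20/80 | Loss (points) |
|---|---|---|---|---|
| 0.1 | 10.4% | 8.4% | 7.6% | 2–3 |
| 0.2 | 27.8% | 19.2% | 15.8% | 9–12 |
| 0.3 | 56.0% | 38.0% | 30.2% | 18–26 |
| 0.4 | 83.3% | 61.8% | 49.9% | 22–34 |
| 0.5 | 97.2% | 83.1% | 70.8% | 14–27 |
| 0.6 | 99.9% | 95.5% | 87.4% | 4–13 |

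Simulation with 20,000 runs per r, for r from 0.2 to 0.5, agrees closely: about 13 to 33 points over r = 0.3 to 0.5. A 10/90 split would lose up to 47 points.

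**Age in six bands.** Assume mean 50 and SD 12, truncated at 18. The six bands keep about 94% of the variance of age, so grouping by itself costs little. The cost depends on the test. The 5-df test uses λ = n·0.935r²/(1 − 0.935r²) with 5 and 41 df. The trend test uses the same λ with 1 and 45 df.

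| Assumed r | Continuous | Trend over bands (1 df) | Omnibus over bands (5 df) |
|---|---|---|---|
| 0.3 | 56.0% | 52.9% | 27.7% |
| 0.4 | 83.3% | 80.3% | 51.7% |
| 0.5 | 97.2% | 95.9% | 79.0% |

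The omnibus test loses 28, 32 and 18 points; the trend test loses 3, 3 and 1. Simulation of the omnibus test, in which some bands are empty, gives slightly smaller losses of 17 to 29 points. The average band holds 47/6 = 7.8 patients; under the assumed distribution the oldest band would hold about one.

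**Sample size.** The figure of 47 rests on the protocol. The SAP gives 55 patients (sections 3.1 and 3.2) and 100 (section 4, with 13% drop-out). With about 50 evaluable (55 × 0.9 = 49.5), the severity loss at r = 0.3 to 0.5 is about 12 to 33 points. With 87 (100 × 0.87) it is about 2 to 32 points. These totals need reconciling.

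**The case against.** The strongest reply is that no section says that Table 11 uses categories. A linear model accepts continuous terms, SAP 3.5.2 lists age at baseline as well as age groups, and the shell cannot be seen. This stands in part: the coding is implied, not stated. But a test across subgroups needs groups, and for severity the documents offer only one split of the enrolled range.

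A reader might be tempted to go further in three ways, none of which the documents support:

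- **That the plan loses a known 14 to 34 points of power.** The correlation and the severity split are assumptions; a weak or a very strong gradient gives a smaller loss. The calculation also tests one modifier alone, whereas Table 11 is multivariable, so the absolute powers do not describe that model.
- **That the six age bands are the Table 11 coding and discard a third of the information.** The bands belong to the descriptive table and keep about 94% of the variance under the assumed distribution. The large loss comes only from a 5-df test that no section specifies.
- **That Table 11 is the only analysis of who benefits more.** The ANCOVA on continuous DAS28 already gives a severity slope for HAQ DI change at weeks 12 and 24, and Protocol 9.7.3 plans further subgroup analyses. What Table 11 adds is mainly age, gender and comorbidity, and severity for the secondary outcomes.

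It is also fair to say that DAS28 classes are easy to read, that a straight line can miss a threshold, and that power at r = 0.3 is only 56% even with continuous terms.

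**Conclusion.** The point holds as a cheap improvement to an exploratory analysis. Table 11 leaves the coding of age and baseline severity open, its wording leans towards categories (more for severity than for age), and that sits badly with the SAP's own use of continuous DAS28.

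If severity is cut in two, the loss with about 47 patients is about 14 to 34 points at assumed r = 0.3 to 0.5 and splits from 50/50 to 20/80, 9 to 12 points at r = 0.2, and 2 to 3 at r = 0.1, given a linear gradient. For age, the loss at r = 0.3 to 0.5 is about 18 to 32 points with a 5-df test over the six bands and about 1 to 3 with a trend test. The primary result is not affected.

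**What to change.** In SAP 5.5 (Table 11) and Protocol 9.7.9, state that age in years and baseline DAS28 enter the model as continuous covariates, as DAS28 does in the ANCOVA of SAP 5.3. Report the modifying effects as slopes per 10 years and per DAS28 unit, with 95% confidence intervals. Gender and comorbidity stay categorical. Keep the moderate/severe and age-band summaries as descriptive displays.

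The cost is one sentence in each document and an edit to the Table 11 shell, with no new data. The downside is the linearity assumption; the retained subgroup summaries would help to show a departure from it.
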